- Transvaginal ultrasound, with or without transabdominal ultrasound, and with or without saline or gel contrast, is performed to determine uterine and myoma volumes and to exclude any other uterine or pelvic pathology. To avoid inter-observer and inter-device variations, a single operator will be assigned to a patient and will perform each of the ultrasound scans using the same device as far as possible. Once the transvaginal ultrasound is done, a transabdominal ultrasound may also be done if the uterus cannot be adequately imaged on transvaginal ultrasound; for example, due to enlarged size. Results must be submitted to a central reader.
- ⁿ Bone densitometry (L1-L4, total hip, femoral neck) will be submitted for central reading.
- This procedure is not required at the Early Termination visit in patients whose last dose of study drug was taken during Week 60 or earlier. However, the procedure may be done if it will aid in the evaluation of an ongoing adverse event.
- Patients with a bone mineral density loss of > 7% at their Week 104/Early Termination visit relative to Parent study Baseline measurement will undergo a follow-up bone densitometry scan at 6 (± 1) months and will be contacted to question them about medications and conditions (estradiol, pregnancy) that might affect bone mineral density through the time of follow-up bone densitometry. The follow-up bone densitometry will be submitted for central reading.
- Patients will be dispensed randomized treatment at the Week 52/Baseline visit, for self-administration beginning the following day, Week 52, Day 1. Randomized treatment will be dispensed at subsequent visits until HMB (MBL ≥ 80 mL) is documented by alkaline hematin testing. When HMB has been documented, the patient will be invited for a visit to begin retreatment with open-label study drug. The timing of that visit should be within 7 days of the onset of the patient's next menses (Cycle day 1-7 where Cycle day 1 is the first day of menstrual bleeding).
- Patients will take the first dose of study drugs for this study once daily starting at Week 52, Day 1 (self-administered with phone follow-up). The last dose of study drug will be taken in the clinic during the Week 104/Early Termination visit.
- s Site to call patient and confirm first dose of study drug was taken that day.
- Patients enter diary information on menstruation status and feminine product use.

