transvaginal ultrasound, and endometrial biopsy (only if required). When Week 52/Baseline procedures in the OLE study have been completed, the investigator will assess patient eligibility for participation in this study. The eligibility assessment will be based on data available at the Week 52/Baseline visit. No study procedures will be performed until the consent form is signed. Patients will receive the last dose of study drug in the OLE study on the day of the Week 52/Baseline visit (per the OLE protocol) and will be dispensed study drug for this Randomized Withdrawal study in the clinic after the patient is determined to be eligible for this study and has provided informed consent to participate. The first dose of study drug for the Randomized Withdrawal study will be self-administered the next morning following the Week 52/Baseline visit. Dosing will be confirmed by telephone.

Post-baseline Procedures: All post-baseline procedures are provided in the Schedule of Activities (Table 1-1).

Patients will be asked to provide feminine products for alkaline hematin analysis at each visit until the analysis confirms the return of heavy menstrual bleeding (defined as menstrual blood loss of ≥ 80 mL). The patients will then be offered retreatment with open-label relugolix with E2/NETA (latter also referred to as "add-back" in context of hormonal "add-back") with the onset of the next menses. They will resume collection of feminine products for alkaline hematin analysis until two consecutive analyses confirm resolution of heavy menstrual bleeding (menstrual blood loss of < 80 mL). Patients who experience a return of heavy menstrual bleeding (or terminate early because they have a return of heavy menstrual bleeding) but decline retreatment with open-label study drug will complete an Early Termination visit and a 30-day Safety Follow-up visit.

At the Week 104/Early Termination visit, all other patients will have an assessment of bone mineral density via dual-energy x-ray absorptiometry (DXA). Patients will complete the bleeding diary daily including compliance with study drug, vaginal bleeding, and use of feminine products.

The pharmacodynamic effect of withdrawal from relugolix with E2/NETA will be characterized by measuring the pre-dose concentration of estradiol at Week 56.

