- If an iron deficiency anemia related to heavy menstrual bleeding develops with a hemoglobin < 8g/dL and is unresponsive to iron supplementation;
- QT interval by the Fridericia correction (QTcF) prolongation of more than 500 msec read by a cardiologist;
- Evidence of endometrial hyperplasia or endometrial carcinoma on endometrial biopsy;
- If the patient has a Z-score < -2.0 or has a \ge 7% decrease in bone mineral density from the Parent study Baseline at lumbar spine, total hip, or femoral neck based on the OLE study Week 52 DXA assessment of bone mineral density;
- If the patient, in the opinion of the investigator or the medical monitor, is grossly noncompliant with the protocol's requirements. This may include < 75% compliance with the study drug for at least 2 months; not returning any feminine products despite having menstrual bleeding for > 2 consecutive cycles; or missing multiple study visits;
- If the patient becomes pregnant at any time after providing a signed informed consent form, the patient must be withdrawn immediately (see Section 7.8 for information on pregnancy reporting).

Should a patient fail to attend the clinic for a required study visit within the protocol-defined window, the site should attempt to contact the patient and reschedule the missed visit as soon as possible. The site should also counsel the patient on the importance of maintaining the assigned visit schedule and determine whether the patient can and/or should continue in the study based on previous noncompliance. In cases where the patient does not return for the rescheduled visit or cannot be reached to reschedule the missed visit, the site should make every effort to regain contact with the patient. The site should make at least 3 documented attempts to contact the subject by telephone, or if necessary by certified letter so that they can appropriately be withdrawn from the study with a primary reason of "Lost to Follow-up."

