ECGs (12-lead) will be obtained at Week 52/Baseline visit in this study, as well as if needed to evaluate any signs or symptom that require an ECG to assess. ECGs will be measured using standardized equipment provided by central core laboratory with the patient in a semi-supine or supine position after 5 minutes of rest. The ECGs will be assessed by central review and a report provided to the site. The investigator or sub-investigator (or a qualified individual at the investigational site) will interpret the ECG report provided by the central reviewer using one of the following categories: normal or abnormal. The investigator or sub-investigator will judge if any of the findings are clinically significant. Any ECGs performed after the Week 52/Baseline visit will be read locally.

6.5.2.6. **Bone Mineral Density**

Bone mineral density is determined using DXA scanning and will be assessed at the lumbar spine (L1, L2, L3, and L4), total hip, and femoral neck (same leg within each patient). Training, quality review, and readings will be done by a central radiology laboratory as described in the central radiology charter for bone mineral density.

Throughout the study, the same DXA apparatus will be used at each site and operated in the same scan mode for all scans for each patient. This should be the same as used for the patient during the OLE study. A central core imaging laboratory will collect and evaluate all DXA scans for acceptability and will have bone mineral density assessed as per the imaging charter. Data from the DXA scans will be managed and analyzed separately by the core laboratory and integrated into the study's database at the end of the study. Bone mineral density changes for individual subjects will be monitored by a central radiology laboratory over the course of the study.

Patients who experience a bone mineral density loss of $\geq 7\%$ from the Parent study baseline at any of the anatomical sites assessed will be discontinued from the study and will undergo another bone densitometry scan as described below. Patients should be assessed for secondary causes of bone loss and followed-up further if not improving on 6 months follow-up scan unless an alternative etiology has been identified.

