
 Disease-specific quality of life as assessed by the Uterine Fibroid Symptom and Health-Related Quality of Life (UFS-QoL) questionnaire 	
 Change from Week 52/Baseline in the UFS-QoL scale and sub-scale scores as well as the total score.
Pharmacodynamic	

 To characterize the pharmacodynamic (PD) effect of withdrawal from relugolix + E2/NETA 	
 Pre-dose concentration of estradiol at Week 56
Safety	

 To evaluate the safety and tolerability of relugolix + E2/NETA, once daily, for up to an additional 52 weeks 	The following safety endpoints will be assessed:

 Adverse events 	
 Incidence of adverse events; Change in vital signs; Clinical laboratory tests.

 Changes in bone mineral density 	
 Percent change from Week 52/Baseline to Week 104 in bone mineral density at the lumbar spine (L1-L4), femoral neck, and total hip as assessed by DXA. Change from Week 52/Baseline to Week 104 in bone mineral density Z-score at the lumbar spine (L1-L4), femoral neck, and total hip as assessed by DXA. Percent change from pivotal study Baseline to Week 104 in bone mineral density at the lumbar spine (L1-L4), femoral neck, and total hip as assessed by DXA.

Abbreviations: DXA = dual-energy x-ray absorptiometry; E2 = estradiol; EOT = End of Treatment; HMB = heavy menstrual bleeding; MBL = menstrual blood loss; NETA = norethindrone acetate; PGA = Patient Global Assessment; UFS-QoL = Uterine Fibroid Symptom and Health-Related Quality of Life; WPAI-UF = Work Productivity Activity Impairment-Uterine Fibroids.

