4.4.1. By-Visit Endpoints

By-visit endpoints will be analyzed using observed data, unless otherwise specified. For observed data analyses, missing data will not be imputed and only the observed records will be included.

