9.3.3.1. Analysis Using Week 52/Baseline Bone Mineral Density as Baseline

As defined in Section 4.3.6, the BMD at Week 52 of the extension study will be used as the Week 52/Baseline in the randomized withdrawal study as long as it was within 30 days of the first dose date of the randomized study drug. If there are multiple BMD measurements at Week 52 in the extension study, the one closest to the first dose date of the study drug will be used as Week 52/Baseline in the randomized withdrawal study.

BMD at Week 52/Baseline and Week 104 visit will be summarized descriptively by treatment group and each measured anatomical location for all patients in the safety population. Percentage changes from Week 52/Baseline along with 95% CIs of mean percentage changes also will be summarized by treatment group and anatomical location. Mean percentage change from Week 52/Baseline with its corresponding 95% CI will be plotted by visit, treatment group, and anatomical location.

An analysis of covariance (ANCOVA) model will be used to assess BMD at Week 104. The model will include treatment, stratification factors (menstrual blood loss volume at pivotal study baseline, and duration of relugolix exposure prior to randomization), race (African American versus Other) as fixed factors, and age at Week 52/Baseline, Week 52/Baseline BMD value, and BMI at Week 52/Baseline as covariates. Least square means on each anatomical location will be presented and plotted with associated 95% CIs. Taking into consideration of the BMD data collected for patients who prematurely discontinued prior to Week 104, the ANCOVA model analysis will also be performed similarly to assess BMD at Week 104/EOT.

Categorical representation of percentage change from Week 52/Baseline to Week 104 (also Week 104/EOT) will be presented by the number and proportion of patients who had BMD increase $> 0\%$, no change (0%), declines of $\leq 2\%$, $>2\%$ to 3% , $> 3\%$ to 5% , $> 5\%$ to 8% , and $> 8\%$ by pivotal study treatment group and anatomical location. The 95% CIs will be provided for the respective proportions.

Categorical changes from Week 52/Baseline in overall BMD (defined as lumbar spine and total hip) also will be assessed. Femoral neck evaluates a smaller area of bone mass than the total hip and is prone to lower precision in the measurement (Leslie et al. 2007; ISCD 2015). Since

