9.3.3.2. Analysis Using the Pivotal Study Baseline Bone Mineral Density as Baseline

For the visits in pivotal and extension studies, the visit window specified in the extension study SAP Table 3 will be used where the first dose of pivotal study drug was used as the reference.

Percentage changes from pivotal study baseline along with 95% CIs of mean percentage changes since first dose of the pivotal study drug at all the timepoints when BMD was scheduled to be collected in a pivotal study, extension study and the randomized withdrawal study also will be summarized by treatment group and anatomical location. Mean percentage change from pivotal study baseline with its corresponding 95% CI will be plotted by visit, treatment group, and anatomical location.

Categorical representation of percentage change from pivotal study baseline to all the timepoints where BMD was scheduled to be collected since pivotal study baseline will be presented by the number and proportion of patients who had BMD increase $> 0\%$, no change (0%), declines of $\leq 2\%$, $> 2\%$ to 3% , $> 3\%$ to 5% , $> 5\%$ to 8% , and $> 8\%$ by treatment group and anatomical location. The 95% CIs will be provided for the respective proportions.

Categorical changes from pivotal baseline in overall BMD (defined as lumbar spine and total hip) also will be assessed at all the timepoints where BMD was scheduled to be collected since pivotal study baseline.

Corrected BMD Z-scores and its change from pivotal study baseline will be summarized by treatment group, visit, and anatomical location with descriptive statistics including 95% CIs, and the number and percentage of patients with a corrected BMD Z-score < -2.0 will be presented by treatment group, visit, and anatomical location. Additionally, categorical change from pivotal study baseline in Z-score will be summarized as ≥ 0 , < 0 to -0.25 , < -0.25 to -0.5 , < -0.5 to -0.75 , < -0.75 to -1 , < -1 to -2 and < -2 , by treatment group, visit and anatomical location.

These analyses will be carried out by six combined analysis groups where the pivotal study treatment group, LTE study treatment and the randomized withdrawal study treatment group are considered (see the [Table 20](#) below).

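### SAP 9.3.3.2 and 9.3.3.3 lose at Week 104 any randomized woman permanently removed for a Week 52 BMD loss of 7% or more, so within-group two-year loss will tend to look too small

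*SAP*

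**What the plan says.** SAP Table 1 adds a safety endpoint that is not in the protocol: "Percent change from pivotal study Baseline to Week 104 in bone mineral density". SAP 9.3.3.2 reports it as means with 95% CIs, decline categories and Z-scores, "at all the timepoints when BMD was scheduled to be collected in a pivotal study, extension study and the randomized withdrawal study", by the six treatment-sequence groups of SAP Table 20 and by prior-monotherapy status. SAP 9.3.3.3 repeats the description with pivotal Week 12 as baseline.

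SAP 4.1 does not impute safety data unless otherwise specified, and SAP 4.4.1 adds: "For observed data analyses, missing data will not be imputed and only the observed records will be included". SAP Table 3 has one BMD window in this study, Week 104, Day 281 to 449. The text after it drops scans taken more than 60 days after the last dose.

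The removal rule uses the same scale. Protocol 4.5 (Amendment 1) lists a decrease of 7% or more from the Parent study baseline at spine, total hip or femoral neck, "based on the OLE study Week 52 DXA assessment of bone mineral density". Protocol 6.5.2.6 says women with that loss "from the Parent study baseline at any of the anatomical sites assessed will be discontinued from the study", and SAP 3.3 repeats it.

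On entry, Protocol 4.1 states "The eligibility assessment will be based on data available at the Week 52/Baseline visit", while DXA scans are read centrally. On leaving, the footnote to Protocol Table 1-1 states "This procedure is not required at the Early Termination visit in patients whose last dose of study drug was taken during Week 60 or earlier".

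For change from Week 52 only, SAP 9.3.3.1 allows for women who stopped early: "the ANCOVA model analysis will also be performed similarly to assess BMD at Week 104/EOT". Sections 9.3.3.2 and 9.3.3.3 have no such version.

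**The concern.** The Week 104 column is selected on an earlier value of the outcome it reports. The women with the largest loss at Week 52 are the ones the protocol stops, and they have no route into the Week 104 summary. A reader who follows a group from its Week 52 to its Week 104 column compares two different sets of women, the second without the worst losers. Mean loss then looks smaller, the curve may seem to flatten, and the top decline categories (more than 5% to 8%, and more than 8%) are thinned.

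This matters because the study's stated aim is safety for up to 104 weeks, and change from pivotal baseline is the analysis that spans that period. The prior-monotherapy comparison (Groups 3 and 4 against the rest) is also exposed. If delayed E2/NETA left those women with greater loss at Week 52, more of them are removed and the difference shrinks.

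**Working it through.** **Can a removed woman reach the Week 104 column?** All inputs are from SAP Table 3, the text after it and SAP 3.3.
- The earliest last dose that allows a Week 104 scan is Day 281 − 60 = Day 221. That is (221 − 1)/7 = 31.4 weeks after first dose, about study Week 83.
- A last dose at Week 60 (about Day 57 to 63) allows usable scans only to Day 117 to 123.
- The follow-up scan at 6 (± 1) months comes at the earliest 5 × 30.4375 = 152 days after last dose, past the 60-day limit.

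So a woman permanently stopped because of her Week 52 scan cannot contribute, unless more than 31 weeks pass before the result is acted on. She remains in the Safety population (SAP 4.2.3) and in the Week 52 column.

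**Size.** The plan states no figure to reproduce: it gives no BMD mean, SD, correlation or expected number removed. All values below are assumptions.

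*One site.* With Week 52 change normal (mean μ, SD σ), correlation ρ between Week 52 and Week 104, and a = (−7 − μ)/σ:
- share removed = Φ(a)
- shift in the Week 104 mean among women kept = ρσφ(a)/(1 − Φ(a))

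Middle case μ = −1, σ = 3, ρ = 0.7: a = −2, removed 2.3% (8 of 360), shift 0.7 × 3 × 0.0540/0.9772 = 0.12 points. Over μ from −0.5 to −3, σ from 2.5 to 4 and ρ from 0.5 to 0.9, removal runs from 0.5% to 15.9% (2 to 57 of 360) and the shift from 0.02 to 1.04 points.

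*Any of three sites,* as the rule is written. Simulation of 400,000 women per scenario: same Week 52 mean at each site, femoral neck SD 1.2 times the others, between-site correlation 0.4, further mean change −0.5. Everyone who meets the rule is taken as randomized, dosed and permanently removed. Spine results:

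| μ, σ, ρ | Removed | Shift in mean, loss continues | Shift if removed women regain 2 points | Share with > 8% loss: all → kept |
|---|---|---|---|---|
| −0.5, 2.5, 0.5 | 2.3% | 0.04 | −0.01 | 0.25% → 0.21% |
| −1, 3, 0.7 | 8.1% | 0.21 | 0.05 | 1.5% → 0.9% |
| −2, 3, 0.7 | 14.6% | 0.35 | 0.06 | 3.3% → 1.7% |
| −2, 4, 0.7 | 27.1% | 0.84 | 0.29 | 8.4% → 3.9% |
| −3, 4, 0.9 | 36.7% | 1.44 | 0.70 | 13.0% → 2.6% |

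*If only some are randomized.* Let p be the share meeting the rule and q the fraction of them randomized. The share removed among randomized women is f = qp/(1 − p + qp), and the shift scales by f/p. Middle case, q = 0.25: f = 0.0202/0.9394 = 0.0215, ratio 0.0215/0.0808 = 0.266, shift 0.2113 × 0.266 = 0.06 points. At q = 0 the shift is zero.

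*Prior-monotherapy contrast.* Suppose one group has a Week 52 mean of −2 and the other −1 (σ = 3, ρ = 0.7). The Week 104 difference in all women is 2.50 − 1.50 = 1.00 point; among women kept it is 2.14 − 1.29 = 0.85.

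**The case against.** Much of the case on the other side stands.

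- **Entry.** Exclusion criterion 10 bars anyone who met a withdrawal criterion in the OLE study. The OLE criteria are not in the documents. If they include a BMD rule, some or all of these women are never randomized. Against that, a rule in Protocol 4.5 keyed to the Week 52 scan has a purpose mainly if some women start dosing before the result is acted on.
- **Permanence.** Protocol 4.5 allows removal to be temporary until the cause is resolved, so some women may resume and have a Week 104 scan. Section 6.5.2.6 and SAP 3.3 do not say this.
- **Visibility.** The losses are not hidden. They appear in the Week 52 column, discontinuation reasons are tabulated (SAP 5.1), and follow-up scans are listed. SAP 3.3 also promises an addendum, though the end of 9.3.3.3 makes the BMD summary optional. None of this repairs the Week 104 column.
- **Target.** The larger shifts assume that removed women would have gone on losing bone as the others did. Protocol Table 7-2 calls the loss reversible. With a 2-point recovery the middle-case shift falls from 0.21 to 0.05.
- **Precision.** With 360 × 0.8/6 = 48 scanned women per group (equal groups assumed) and SD 3, the CI half-width is 1.96 × 3/√48 = 0.85 points, above most of the shifts. But the shift is systematic, and the interval does not allow for it.

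A reader might infer that two-year loss is understated as a matter of fact, by a known percentage. The documents do not support that: no removal count or BMD distribution is given. A reader might also infer that the comparison of relugolix + E2/NETA with placebo is biased. The Week 52 scan precedes randomization and the rule applies to both arms alike, so that contrast is less affected. Nor is the summary limited to women who attend a Week 104 visit; late early-termination scans from Day 281 also count.

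**Conclusion.** The selection is built into the plan and follows from the documents. A randomized woman permanently removed on her Week 52 scan is counted at Week 52 and cannot be counted at Week 104, and 9.3.3.2 and 9.3.3.3 lack the early-discontinuation version that 9.3.3.1 has. For on-treatment loss within groups the direction is towards understatement in every scenario with positive correlation between the two scans.

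The size cannot be established. Under the assumed inputs it runs from about zero (few such women enrolled, or mild loss with recovery) through 0.21 points in the middle case to more than 1 point at the extreme. The exposed results are the within-group two-year means, the upper decline categories and the prior-monotherapy comparison. In 9.3.3.3 the same women are missing, although the removal rule is measured from pivotal baseline and not from Week 12. The point is worth correcting in the SAP; it does not touch the efficacy conclusions.

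**What to change.** In SAP 9.3.3.2 and 9.3.3.3, keep the observed-case tables and add:

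1. A Week 104/EOT summary (means and, in 9.3.3.2, decline categories) for the Safety population, using each woman's last available on-study scan. Where there is no later scan, the Week 52 scan serves as the last value. This extends the idea already in 9.3.3.1; without the fallback it would still miss women who have no scan after Week 52. A last-scan rule is preferable to a worst-scan rule, which takes an extreme over noisy scans that differ in number between women.
2. By combined analysis group, the number removed under the BMD rule, and the Week 52 mean with and without the women who lack a Week 104 scan.
3. As a supportive analysis, a repeated-measures model on all BMD visits from the pivotal study onward, by combined analysis group. State that it assumes missing at random given earlier scans and that it estimates loss had treatment continued. SAP 7.1.2 rules out mixed models only for the randomized treatment period and uses them for the cumulative period, so it is no bar here.

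The following passages must be reconciled:
- Protocol 4.5 (temporary or permanent removal) with 6.5.2.6 and SAP 3.3 (discontinued from the study);
- the waiver of the Early Termination DXA, Week 56 in Protocol 6.3 and Week 60 in the footnote to Table 1-1;
- SAP 3.3 (follow-up data will be summarized) with the end of 9.3.3.3 (may be).

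The analysis changes cost SAP wording and a few tables from data already held, with no new scans. The downside is that the reported two-year loss may look slightly worse.
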